Comparison of training effect for tracheal intubation following training with McGrath video laryngoscope as direct laryngoscope versus training with McGrath video laryngoscope as video laryngoscope

NCT03471975

March 01 2018

Brief Title: Learning Direct Laryngoscopy Using a McGrath Video Laryngoscope as Direct Versus Indirect Laryngoscope

Official Title: Comparison of training effect for tracheal intubation following training with McGrath video laryngoscope as direct laryngoscope versus training with McGrath video laryngoscope as video laryngoscope

Study Type: Intervention

Principal Investigator: [name]., Ajou University School Of Medicine, [contact]

Objective

Tracheal intubation using a direct laryngoscope is an essential skill but is difficult to teach. Video laryngoscopes enhance the teaching ability for direct laryngoscopy and can be used with direct or indirect methods. We compared the effect on the skill improvement of Macintosh direct laryngoscopy following training with a McGrath video laryngoscope as a direct versus an indirect laryngoscope.

Design

prospective, cluster-randomized controlled trial

Methods

This study was a single-center, prospective, cluster-randomized controlled trial with two parallel groups that was carried out at Ajou University Hospital from March 2018 to July 2018. The trial was approved by the institutional review board of Ajou University Hospital (AJIRB-SBR-OBS-17-507, Feb 20, 2018) and was registered at ClinicalTrials.gov (NCT03471975).

Eligible participants were medical students who are novices at direct laryngoscopy. All of the participants agreed to have their performances evaluated and anonymously used for scientific and educational purposes.

Rotation groups (including 11 groups that each included 3–4 students) were randomly divided into one of two groups in ratio of 1:1 by the cluster randomization method, using a computer-generated random number table. The allocation process was conducted by a colleague who remained independent of this research project. The randomization result was concealed within serially numbered opaque envelopes, which were opened prior to teaching and lecture. One group was trained using direct laryngoscopy with a video laryngoscope (direct group), and the other group was trained using indirect (video) laryngoscopy with a video laryngoscope (indirect group). Cluster randomization was adopted to eliminate possible contamination between students due to individual randomization within each rotation. The blinding of participants and instructors was not possible due to the nature of the interventions

The study took place on the first day of the rotation. First, an initial evaluation of the students' intubation skills was performed on a standardized manikin (Laerdal® Airway Management Trainer, Laerdal, Stavanger, Norway) using a Macintosh laryngoscope (Diamond range; Penlon, Abingdon, UK; Macintosh blade size 3). The instructor evaluated each attempt and gave no feedback. Then, a lecture on airway anatomy, evaluation, and Cormack-Lehane classification (degree of glottis exposure), as well as airway management, was given, followed by tutorial videos on the technique of direct laryngoscopy and introduction of the McGrath[™] MAC video laryngoscope

(Medtronic, Minneapolis, MN, USA). Following the lecture, a teaching sequence with the McGrath[™] MAC video laryngoscope was conducted. All participants performed five intubations in the manikin using the McGrath[™] MAC video laryngoscope (blade size 3) with the instructor's direct feedback. The direct group intubated using the video laryngoscope as a direct laryngoscope, where only the instructor could observe the video screen and give feedback. The indirect group used the video laryngoscope as an indirect laryngoscope, so that they shared the video view with the instructor and received feedback.

Then, a final evaluation was performed in which the students performed tracheal intubation using the Macintosh direct laryngoscope in the same manikin in the following scenarios: 1) normal airway in the supine position and 2) cervical immobilization with a semi-rigid foam neck collar (Philadelphia cervical collar; A-Mi Global, Busan, South Korea). Each student performed the intubation twice for each scenario, and the instructor evaluated each attempt. For all intubation attempts, a standard beveled Portex® tracheal tube (Smiths Medical, Hythe, UK; 7.0 mm internal diameter, 9.6 mm outer diameter) was used with a stylet inserted in the tube. The tube was bent into a "hockey-stick" curvature. The outcome assessors did not involve in training and were kept blinded to the allocation.

The primary endpoint was the intubation time, defined as the time taken from insertion of the blade between the teeth until the cuff of the tube was inflated. Unilateral bronchial intubation was considered successful for the purpose of this study. A failed intubation was defined as when it was not completed within 120 seconds or it resulted in an esophageal intubation. Additional data obtained included the rate of successful tracheal intubation, dental trauma, and degree of difficulty. Dental trauma was counted based on the number of audible teeth clicks (0, 1, and 2) in the Laerdal airway trainer. After the students completed the attempts, they were asked to score the degree of difficulty using each device with a 10-point numeric rating scale (NRS; 0 = easy, 10 = difficult).

Statistical Analysis Plan

All statistical analyses were performed using SAS version 9.4 (SAS Institute, Inc., Cary, NC, USA).

Data are presented as the mean and SD when normally distributed, as the median and interquartile range when non-normally distributed, and percentage when appropriate.

We used the linear mixed effects model to analyze intubation times and the degree of difficulty.

We also applied the generalized linear mixed model with binomial distribution and generalized estimating equations methods to analyze the intubation success rate.

As fixed effects, we included baseline intubation time, age, sex, group, manikin, time, and time by group interactions.

As random effects, we used a random intercept and slope for intubation time after education and a random intercept only for the degree of difficulty.

The variance-covariance structures were chosen with the smallest Akaike Information Criterion criteria. In regard to the selection of working correlation matrix in the generalized estimating equations model, Quasi-likelihood under the Independence model Criterion was used to assess the goodness-of-fit. We also specified and partitioned different variance-covariance structures for each level of manikin. For comparing times before training with those after training, we used the paired t-test, Mann-Whitney U test, or McNemar's test, as appropriate. A *p*-value < 0.05 was considered statistically significant.

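### The allocation envelope is opened before the teaching common to both arms, and not clearly after the baseline evaluation: an avoidable risk of bias, though not a demonstrated one

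*Combined protocol and SAP*

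**What the plan says.** All of this is in the Methods section of the combined protocol and SAP, unless another section is named.

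- **Opening of the envelope.** The allocation was "concealed within serially numbered opaque envelopes, which were opened prior to teaching and lecture".
- **Blinding.** "The blinding of participants and instructors was not possible due to the nature of the interventions".
- **Order of the day.** Each student first does an initial Macintosh intubation on the manikin, scored by the instructor without feedback. A lecture on the airway comes second, and tutorial videos on direct laryngoscopy with an introduction of the McGrath come third; neither is described as differing by arm. The training step comes last: "Following the lecture, a teaching sequence with the McGrath" device.
- **Where the arms differ.** All students do five McGrath intubations "with the instructor's direct feedback". The direct group uses the device "where only the instructor could observe the video screen and give feedback"; the indirect group uses it "so that they shared the video view with the instructor and received feedback".
- **Assessment and analysis.** Outcome assessors are said to be blinded and to have had no part in the training. The Statistical Analysis Plan lists baseline intubation time among the fixed effects.

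**The concern.** The trial is meant to compare two ways of using the McGrath during five training intubations. Everything before that step should be the same in both arms. Opening the envelope before the lecture allows the person lecturing, and possibly the students, to go through the common phase knowing the arm. That phase bears on the tested skill: the videos teach direct laryngoscopy, and the primary endpoint is intubation time with a Macintosh direct laryngoscope.

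A lecturer who knows the arm could, without intent, shift emphasis in live remarks or in introducing the device. Where a rotation group is taught together, the shift would reach the whole group. A shift that follows the arm would then be counted as an effect of the training method.

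A second, smaller issue is the baseline. If the envelope were opened before the initial evaluation, the baseline time used for adjustment could also be influenced by knowledge of the arm.

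**Working it through.** No arithmetic applies beyond a count. The document gives no figure that depends on when the envelope is opened, so the check sets the order of events against the opening rule and the blinding statements.

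**Step 1: when is the arm needed?** The day has four parts before the final evaluation.

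| Part | Differs by arm as described? | Arm needed to carry it out? |
|---|---|---|
| Initial Macintosh evaluation | No | No |
| Lecture | No | No |
| Tutorial videos and McGrath introduction | No | No |
| Five McGrath intubations with feedback | Yes | Yes |

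The arm is first needed at the fourth part.

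**Step 2: when is it revealed?** Before the lecture, so at the latest before the second part. The wording fixes only this latest point. It sets no earliest point, so opening before the initial evaluation is not excluded.

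**Step 3: does the stated reason cover the gap?** Blinding is called impossible because of the nature of the interventions. That holds for the five intubations, where student and instructor must know who may see the screen. It does not hold for the first three parts, which are the same in both arms.

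**Step 4: is there a safeguard in the gap?** The document does not say that the lecture was scripted, or that it was given by someone unaware of the arm. It also does not say who opened the envelope or when students were told. The videos, as recorded material, leave little room for differential delivery. The live parts, meaning the lecture and the introduction of the device, leave more.

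**Step 5: could the analysis remove such a difference?** The fixed effects besides group and its interaction with time are baseline intubation time, age, sex, manikin and time. None measures how the common content was delivered. A difference in delivery that follows the arm is aliased with the group term, and no random effect would separate the two. Assessor blinding protects the measurement of the outcome, not the delivery of the teaching.

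**Step 6: extent.** The rule applies to all 11 rotation groups of 3 to 4 students, that is 11 × 3 = 33 to 11 × 4 = 44 students. This counts who falls under the rule. It does not measure bias.

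**The case against.** The strongest objections are these.

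- **No difference is documented.** A reader might infer that the contrast is no longer purely direct versus indirect use of the device. The document does not support this: it describes the common content once, for everyone. This objection stands, and only a possible departure can be claimed.
- **Who knew the arm is not stated.** A reader might infer that lecturer and students all went through the common phase knowing the arm. The statement on blinding does not say when they learned it, and the lecturer is not identified. This stands too, but it also means that the plan neither prevents nor records such knowledge.
- **The lecture is not described as teaching technique.** Technique is named under the tutorial videos. This stands, and it narrows the plausible route to live remarks and the device introduction.
- **The training step stays unblinded.** Immediately afterwards, an instructor who must know the arm gives direct feedback on five intubations. Differential emphasis can enter there more directly, and later opening does not change that. This stands as a limit on the benefit. It is no reason to extend unblinding to parts that do not need it.
- **The baseline argument is conditional.** The natural reading puts the opening between the initial evaluation and the lecture, no feedback is given at baseline, and assessors are said to be blinded. This largely stands. However, the text names the instructor as scoring the initial evaluation, so the timing should be stated rather than left to the reader.
- **Concealment is intact.** Allocation was done by an independent colleague and kept in numbered opaque envelopes. This stands: the point concerns delivery of the common content and the baseline, not predictability of the allocation.

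**Conclusion.** The point holds as an avoidable risk. The opening rule reveals the arm before teaching that is described as common, and it does not place the opening after the baseline evaluation. The reason given for not blinding does not extend to either. This conclusion rests on two readings of the Methods: that the lecture, videos and device introduction were meant to be identical in both arms, and that the absence of any stated script or arm-unaware lecturer means none was planned. If either reading is wrong, a sentence saying so would answer most of the point.

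The size and direction of any bias cannot be computed from the document. The text does not support saying that the common content differed by arm, that the baseline was affected, or that later opening would isolate the device-use contrast. The change is worth making because it costs almost nothing, not because harm has been shown.

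**What to change.** Replace the clause on opening with wording such as: *The envelope for each rotation group is opened after the initial evaluation, lecture, tutorial videos and McGrath introduction are complete, immediately before the five training intubations.* Limit the statement that blinding was impossible to that training step, and acknowledge that instructor feedback there remains unblinded.

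The cost is one sentence and a later opening time; the envelopes, staff and day stay the same.

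The Methods are written in the past tense. If sessions have already been run, report when the envelope was opened relative to the initial evaluation, who knew the arm during the common phase, and whether the common content was standardised. Where this cannot be established, state it as a limitation.

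### Must the SAP name the arm contrast, define time and manikin, and fix how the two airway scenarios are weighted?

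*Combined protocol and SAP*

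**What the plan says.** The Objective names no scenario, attempt or weighting: "We compared the effect on the skill improvement of Macintosh direct laryngoscopy following training". Under Methods, the final evaluation is done "using the Macintosh direct laryngoscope in the same manikin in the following scenarios", namely a normal airway and a neck collar. "Each student performed the intubation twice for each scenario", so each student contributes 2 × 2 = 4 post-training times.

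The Statistical Analysis Plan uses a linear mixed model for intubation time, the primary endpoint: "As fixed effects, we included baseline intubation time, age, sex, group, manikin, time, and time by group interactions". For the random part, "we used a random intercept and slope for intubation time after education". On covariance it adds: "The variance-covariance structures were chosen with the smallest Akaike Information Criterion criteria", and "We also specified and partitioned different variance-covariance structures for each level of manikin". Change from before to after training is handled elsewhere: "For comparing times before training with those after training, we used the paired t-test", or one of two alternatives.

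The SAP does not say which coefficient or contrast is the primary arm comparison. It defines neither time nor manikin and has no group-by-manikin term.

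**The concern.** A model containing both group and time-by-group has more than one candidate for the training effect. If time meant before versus after training, the interaction would carry the effect. If time means attempt, the group term carries it, but what the printed group coefficient represents depends on coding. Suppose the arms differed by 10 s at attempt 1 and 2 s at attempt 2 (assumed). The group result could then be 10, 2 or 6 s, and the interaction would be −8 s.

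The second worry is the scenarios. Without a group-by-manikin term, the arm effect at each attempt is forced to be the same in the normal airway and with the collar. If the scenarios have different variances, the mixed model gives more weight to the less variable one, and those weights are known only after fitting. If training helped in one scenario only, the reported seconds would be neither that scenario's effect nor the equal average, and no model term would show the difference.

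**Working it through.** The plan states no effect size, standard deviation or power, so there is no figure to reproduce. The check has two parts.

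**1. What the terms mean.** Baseline time is a covariate, the random effects are for times after education, and before/after change has its own tests. A before/after meaning would make baseline both covariate and outcome. Time is therefore the post-training attempt. Only one manikin is used, so its levels can only be the two scenarios.

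With two attempts per scenario, time as a class variable and time as a number describe the same mean model. Coded 1 and 2, the arm effect is b_g + b_gt at attempt 1 and b_g + 2b_gt at attempt 2, with average b_g + 1.5b_gt. Coding changes which coefficient is printed, not the attempt-averaged contrast.

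**2. How the scenarios are weighted.** Assumed inputs, none from the documents: student-intercept variance 0.4; normal-airway residual variance 0.6; collar residual variance r = 0.6, 1.2 or 2.4; independent students. Clustering by rotation group is left out, so the powers below compare weightings and are not powers for this trial.

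Variances of a student's scenario mean over two attempts:
- normal airway: V1 = 0.4 + 0.6/2 = 0.70
- collar: V2 = 0.4 + r/2 = 0.70, 1.00, 1.60
- covariance between scenarios: C = 0.4 if the random effect is shared, C = 0 if it is partitioned by scenario and independent. The SAP does not say which.

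Formulas:
- normal-airway weight w = (V2 − C)/(V1 + V2 − 2C)
- precision-weighted variance = (V1V2 − C²)/(V1 + V2 − 2C)
- equally weighted variance = (V1 + V2 + 2C)/4
- SE ratio k = √(equal/precision)

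| | r = 0.6 | r = 1.2 | r = 2.4 |
|---|---|---|---|
| C = 0.4: w | 0.30/0.60 = 0.50 | 0.60/0.90 = 0.67 | 1.20/1.50 = 0.80 |
| C = 0.4: equal; precision variance | 0.55; 0.55 | 0.625; 0.60 | 0.775; 0.64 |
| C = 0.4: k | 1.00 | 1.02 | 1.10 |
| C = 0: w | 0.70/1.40 = 0.50 | 1.00/1.70 = 0.59 | 1.60/2.30 = 0.70 |
| C = 0: equal; precision variance | 0.35; 0.35 | 0.425; 0.412 | 0.575; 0.487 |
| C = 0: k | 1.00 | 1.02 | 1.09 |

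If the arms differed by 10 s with the collar and 0 s in the normal airway, the model would report 10(1 − w): 5.0, 3.3 and 2.0 s with C = 0.4, or 5.0, 4.1 and 3.0 s with C = 0. The equal average is 5 s.

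For power, take an effect in one scenario that has 80% power under equal weighting (1.96 + 0.84 = 2.80). Under precision weighting its power is Φ(2.80 × 2 × weight × k − 1.96), using that scenario's weight.

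| | r = 0.6 | r = 1.2 | r = 2.4 |
|---|---|---|---|
| Collar only, C = 0.4 | 80% | 48% | 23% |
| Collar only, C = 0 | 80% | 65% | 46% |
| Normal airway only, C = 0.4 | 80% | 97% | 99.9% |
| Normal airway only, C = 0 | 80% | 92% | 99% |

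If the effect is common to both scenarios and has 80% power under the stated model, equal weighting has Φ(2.80/k − 1.96): 80%, 78% and 72% with C = 0.4.

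These figures omit the random slope. Generalized least squares on the group, manikin, time and time-by-group terms with a shared random intercept and slope (33 students, 18 versus 15; residual SD ratios 1, 1.5, 2 and 3) gives normal-airway weights of 0.50, 0.69, 0.80 and 0.90. They are the same at attempt 1, at attempt 2 and on average. The SD ratio of 2 is the variance ratio 2.4/0.6 = 4 above and gives the same 0.80.

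If the arms do not differ in either scenario, w × 0 + (1 − w) × 0 = 0 for every w.

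**The case for a change.** The strongest case for a change is that nuisance variances, not the training question, choose the weights, and that they move from trial to trial. In 1,000 simulated trials per case (15 and 18 students, shared intercept, no random slope, AIC choosing between common and scenario-specific residual variance), the 5th to 95th percentile of the normal-airway weight was 0.35–0.65, 0.50–0.78 and 0.72–0.88 for the three collar variances. A reader given one figure in seconds cannot tell which scenario it describes. One interaction term and an equally weighted contrast would need no new data.

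Part of this stands. The contrast is unnamed, the two terms are undefined, and a scenario-specific effect could be diluted. But the dilution needs two things that the documents do not show: unequal variances and an arm effect that differs by scenario. It also cuts both ways, since a normal-airway-only effect gains power. Equal weighting has its own cost when the effect is common. Keeping the model and labelling its result a common effect would change no analysis.

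**Conclusion.** No change is needed. The missing definitions are a gap that an analyst fills from context: baseline as a covariate and the separate before/after tests make time the attempt, and the single manikin makes its levels the scenarios. The natural arm comparison is then the baseline-adjusted difference averaged over attempts, which does not depend on coding.

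The scenario weighting is a fair trade-off. For assumed collar residual variances from equal to four times the normal-airway value, the normal-airway weight runs from 0.50 to 0.80. Power for a collar-only effect falls from 80% to as low as 23%, and power for a normal-airway-only effect rises to as much as 99.9%. Equal weighting costs up to 10% in standard error if the effect is common. The test of no arm difference in either scenario remains valid. These sizes rest on assumed variances, independent students and time taken as two attempts within each scenario; with equal variances the weights are 50/50. Nothing in the documents shows that the plan estimates the wrong quantity.

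### Eleven rotation groups are randomised, but no model in the analysis plan is stated to account for rotation group

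*Combined protocol and SAP*

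**What the plan says.** The Methods describe a "single-center, prospective, cluster-randomized controlled trial with two parallel groups". The unit of allocation is explicit: "Rotation groups (including 11 groups that each included 3–4 students) were randomly divided into one of two groups in ratio of 1:1". The reason is given too: "Cluster randomization was adopted to eliminate possible contamination between students due to individual randomization within each rotation". On delivery, the Methods state that "The study took place on the first day of the rotation", with a lecture and instructor-led manikin training, followed by a final evaluation of two attempts in each of two scenarios per student.

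The Statistical Analysis Plan names a linear mixed model for intubation time and difficulty, and a binomial mixed model and GEE for success. Its terms are:

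- Fixed effects: "As fixed effects, we included baseline intubation time, age, sex, group, manikin, time, and time by group interactions". Paired with the interaction, the word group here reads as the training arm.
- Random effects for the primary endpoint: "As random effects, we used a random intercept and slope for intubation time after education". No grouping unit is named.
- Covariance: chosen by AIC, with one partition stated: "We also specified and partitioned different variance-covariance structures for each level of manikin".
- GEE: QIC is to be used "In regard to the selection of working correlation matrix in the generalized estimating equations model". The cluster variable is not named.

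The plan gives no ICC, degrees-of-freedom method or small-sample correction.

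**The concern.** When rotations are randomised, the arm comparison must be judged against variation between rotations. Rotation is nested within arm, so its absence from the fixed effects is not a fault. It could enter as a random effect, through the residual covariance or as the GEE cluster, and none of these is stated to carry it.

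Because each student makes repeated attempts and the slope is for time after education, the random effects read most naturally as student-level. A student effect absorbs correlation among one student's attempts, but not correlation among students in the same rotation. AIC or QIC can help only if rotation is among the candidate structures, and the plan does not say that it is.

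If rotation-mates share a teaching session, some correlation within rotation is plausible. Standard errors for the arm and time-by-group contrasts would then be too small, and the 0.05 threshold would not deliver a 5% error rate for the primary endpoint.

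**Working it through.** The documents give no sample size calculation, SD or ICC, so there is no figure of the plan's own to reproduce. The check asks what a student-level test at 5% does when rotations are the randomised unit.

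**Inputs from the documents:** 11 rotations of 3–4 students, so 11 × 3 = 33 to 11 × 4 = 44 students; 1:1 allocation; significance level 0.05.

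**Assumptions:** two-sided test; ICC from 0 to 0.30; one unadjusted value per student; arms of 5 and 6 rotations. The split is not stated. Under simple randomisation of 11 units, 5/6 has probability 2 × 462/2048 = 45% and 4/7 has 2 × 330/2048 = 32%, so 4/7 was also run.

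**Formulas:** design effect DE = 1 + (m − 1) × ICC for cluster size m; true type I error ≈ 2 × [1 − Φ(1.96/√DE)].

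Example, m = 4 and ICC 0.10: DE = 1 + 3 × 0.10 = 1.30; √1.30 = 1.140; 1.96/1.140 = 1.719; type I error 8.6%.

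| ICC | DE (m = 3 / 4) | Formula, % (m = 3 / 4) | Simulated, % (33 / 38 / 44 students) |
|---|---|---|---|
| 0 | 1.00 / 1.00 | 5.0 / 5.0 | 5.0 / 5.0 / 5.0 |
| 0.01 | 1.02 / 1.03 | 5.2 / 5.4 | 5.1 / 5.4 / 5.5 |
| 0.05 | 1.10 / 1.15 | 6.2 / 6.8 | 6.2 / 6.5 / 6.8 |
| 0.10 | 1.20 / 1.30 | 7.4 / 8.6 | 7.3 / 8.0 / 8.7 |
| 0.20 | 1.40 / 1.60 | 9.8 / 12.1 | 9.9 / 11.1 / 12.6 |
| 0.30 | 1.60 / 1.90 | 12.1 / 15.5 | 12.4 / 14.5 / 16.0 |

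The simulated column uses 100,000 null trials per cell and a 6/5 split. The t-test on 11 rotation means (11 − 2 = 9 df) rejected in 4.9–5.2% of trials in every cell. A second simulation, with sizes 3 or 4 at random and 20,000 trials per cell, gave 6.7%, 8.4% and 14.6% at ICC 0.05, 0.10 and 0.30 for a 5/6 split, and 6.4%, 7.9% and 14.5% for 4/7.

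**Time by group** (one change score per student): a rotation intercept cancels from the change. If rotations also differ in change, student-level type I error is 4.8, 5.5, 6.4, 7.9, 11.4 and 14.5% when 0, 1, 5, 10, 20 and 30% of the change variance lies between rotations. A t-test on rotation mean changes gives 4.6–5.0%.

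**Success rate** (four attempts per student; assumed success 60–80%, student SD 1.0 logit):

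- An uncorrected sandwich variance clustered on student gives 5.5–6.3% with no rotation effect, and 11–12% with an assumed rotation SD of 0.7 logits.
- Clustered on the 11 rotations without correction, it gives 10.3–11.3%, so naming rotation alone would not repair the GEE.
- A t-test on rotation proportions gives 4.7–5.1%.

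**Degrees of freedom:** the ANOVA estimate of rotation variance is zero or negative in 42% of samples at ICC 0.05 and 31% at 0.10. A data-driven df would therefore often revert to a student-level value.

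**The case against.** The strongest reply is that this is an omission, not a demonstrated wrong analysis. Every model named can carry clustering, and the plan names no grouping unit at all, not even student. If rotation was in fact modelled, the defect is one of reporting. That is fair, and it is why the student-level conclusion is conditional. The analysis would still not be reproducible from the plan, and the small-sample question would remain open.

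Second, the harm depends on an unknown ICC, and there are reasons to expect a low one. Training took place on day one, the manikin was standardised, feedback concerned each student's own attempts, and the model adjusts for baseline time, age and sex. The Methods do not say that lectures were given rotation by rotation or that instructors differed. This stands as a limit on size: the figures above 10% for the arm comparison need an ICC of about 0.20 or more. It does not justify leaving the randomised unit unstated.

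Third, time in the model may index repeated attempts after training, not change from before to after, so the time-by-group figures rest on one reading. The success-rate scenario with 0.7 logits implies a within-rotation correlation of about 0.16–0.17, which is at the upper end. Both points are accepted; these figures are illustrations, and the conclusion rests on the arm comparison.

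**Conclusion.** The concern holds. The plan randomises rotations and states no model that accounts for them. On the natural student-level reading, the arm comparison for the primary endpoint is anti-conservative: negligibly at ICC 0–0.01, by one to two percentage points at 0.05, and by roughly 2 to 11 points across ICC 0.10–0.30. Small clusters keep the inflation moderate. The size rests on an assumed ICC and an unadjusted comparison; covariate adjustment may lower the residual ICC. The omission itself rests on neither, and it should be corrected because it affects the primary endpoint and every modelled secondary endpoint.

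**What to change.** - State the level of every random effect and the GEE cluster.
- Add a random intercept for rotation, with students nested in rotation, to the time, difficulty and success mixed models, and keep it whatever AIC prefers.
- For time by group, add a rotation-by-time random effect. Alternatively, test the contrast on rotation-level summaries of change, which also serves if the fuller model cannot be estimated from 11 clusters.
- Refer arm and time-by-group contrasts to about 9 between-cluster df, fixed in advance, including in the binomial mixed model. Report a t-test on the 11 rotation summaries as the check. Do not rely on Kenward-Roger alone, since its df depends on whether the rotation variance is estimated as zero.
- For success, use GEE with rotation as cluster, a small-sample-corrected sandwich variance and a t reference, or analyse rotation-level proportions.

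The plan is written in the past tense. If results are already known, label this as a re-analysis by the randomised unit.

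**Cost:** SAP wording and modest SAS changes, with no new data. The critical t rises from 2.040 (31 df) or 2.018 (42 df) to 2.262 (9 df), ratios of 1.109 and 1.121, so intervals widen by 11–12% even at ICC 0. With DE = 1 + 2.5 × ICC and a ratio of 1.116 at the average size, the widening is √1.125 × 1.116 = 1.18 at ICC 0.05, √1.25 × 1.116 = 1.25 at 0.10, √1.50 × 1.116 = 1.37 at 0.20 and √1.75 × 1.116 = 1.48 at 0.30. At ICC 0.05, most of this comes from the df.

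The mixed-model test with df fixed at 9 is conservative at low ICC (2.0% at ICC 0, 2.7% at 0.05); the t-test on rotation summaries is not. At ICC 0.10, the difference detectable with 80% power rises from 1.01 to 1.21 SD with 33 students, and from 0.87 to 1.09 SD with 44, compared with treating students as individually randomised.
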